### 9.6.3. King's clinical stage of ALS

The course of disease was classified according to the King's clinical stage of ALS (Balendra et al. 2014). Stage 1: involvement of one clinical region; Stage 2: involvement of second clinical region; Stage 3: involvement of third clinical region; Stage 4: nutritional or respiratory failure.

*Table 7: Items used to describe functional deficits and progression*

Item	Description
ALS-FRS	ALS-FRS, total score ALS-FRS, score points per item (1-12)
ALS progression rate	Loss of ALS-FRS score points per month
King's clinical ALS stages	Stage 1-4

Neurofilament light chain (sNfL)	Serum concentration of neurofilament light chain (sNfL) in pg/mL
----------------------------------	--

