## 1. Visit schedule

Table 1: Visit schedule

Visit schedule	V1 M1-M3 (Baseline)	V2 M4-M8* (Follow-Up)	V3 M9-M14 (Closure)
Demographic data			
Age	x		
Gender	x		
Place of residence	x		
Social characteristics			
Employment status	x		
Marital status	x		
Education level	x		
Living arrangement	x		
Disease history			
Date of disease onset	x		
Date of initial diagnosis	x		
Age at disease onset	x		
Duration of disease	x		
Date of death (if applicable)			
Family history			
Family members who are living with ALS	x		
Family members who died of ALS	x		
Family members who are living with FTD	x		
Family members who died of FTD	x		
Family members who are suffering from neurological/psychiatric disorder	x		
Family members who died of any neurological/psychiatric disorder	x		
Clinical classification			
ALS subtypes	x		
Region of onset	x		
Functional deficits and progression			
ALS Functional Rating Scale (ALS-FRS)	x	x(2)	x
ALS progression rate (loss of ALS-FRS per month)	x	x(2)	x
King's classification of clinical stages of ALS	x		x
Serum neurofilament light chain (sNFL)	x	x(2)	X(2)
Interventions and health care measures			
Use of PEG	x		x
Use of non-invasive ventilation	x		x

Use of tracheotomy	x		x
Provision of a manual wheelchair (1)	x		
Provision of complex power wheelchair (1)	x		
Provision of a communication device (1)	x		
Provision of assistive technology (1)	x		
Physical, occupational and speech therapy (1)	x		
Riluzol and symptomatic pharmacotherapy (1)	x		
Treatment expectation			
MYMOP2, measure yourself outcome profile	x	x(2)	x(2)
Molecular genetic analysis			
C9orf72	x		
FUS	x		
SOD1	x		
TARDP	x		

M: month, V: visit; 1 = subgroup of users of APST management platform, 2 = in subgroup of patients with SOD1 mutation data will be collected more frequently (up to monthly collection of existing data of sNfL; up to weekly self-assessment of ALS-FRS using the ALS-App in addition to on-site assessment of ALSFRS-R during site visits). In the main cohort of non-SOD1 patients the collection of sNfL data is limited to the visits V1 (baseline) and V2 (follow-up).

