## **5. Study subjects**

### **5.1. Number of study subjects**

2,000 subjects are planned to be recruited. More than 1000 subjects are expected to complete the end-of-study assessments, after an observation period of 12 months.

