## **11. Statistical methods and analysis plan**

Descriptive statistics will be presented for each assessment of all subjects at study visit. Subgroup analyses by genetic or clinical criteria or other baseline characteristics will be performed. Secondary endpoints in the genetically defined subsets of ALS with confirmed SOD1 or C9orf72 mutations will be compared to genetically tested patients with ALS not revealing any ALS-associated mutation in any of the tested genes. Descriptive statistics will be used for the statistical analysis (frequency in percentage, mean, median, standard deviation in  $\pm$ , interquartile ranges (Q1, Q3), and ranges (min, max). The standardized mean difference (SMD) will be applied in this study. The SMD of each measure over up to 12 months will be estimated using the change in measure between each subject's assessments and within each individual. The standardized mean difference expresses the size of intervention effect. Difference of frequencies between two groups will be assessed by Fisher's exact test or Chi-square test, or within metric data by using the Shapiro-Wilk test, Kruskal-Wallis test and Mann-Whitney U-test. The Wilcoxon test will be employed for the analysis of statistical power of ordinal-scaled data, while metric data were subjected to the t-test (ALS-FRS, MYMOP). This analysis applies to the comparison of genetically defined subsets of ALS (baseline characteristics and changes over time). The analysis of follow-up data is limited to complete

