cases, since not all patients are expected to complete end-of-study assessments due to disease progression, e.g., death. It is aimed to compare the baseline characteristics and the proportion of death between those who completed and not those not completed 6 months and 12-month assessment. Statistical significance will be ascertained by according to an error risk of up to 5% (p-value < 0.05). Associations for the clinical outcomes will be assessed by linear regression models adjusted for potential confounding factors. Results of the longitudinal observations will be also controlled for the influence of any covariate (sex, age, intervention history). Longitudinal analysis by means of group comparisons will be applied by using a multivariate analysis. 95% confidence intervals with p-values will be reported. In order to draw conclusions from the samples with censored data, missing data records will be omitted and treated as missing values. Data analysis will be performed using SPSS (Version 25.0).

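### Any follow-up comparison of King's stage by genotype is confined to survivors: the scale stops at stage 4, V3 is the only later value, deaths drop out, and mortality is never compared by genotype

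*Combined protocol and SAP*

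**What the plan says.** - **Scale.** Section 9.6.3 defines four stages, the last being "Stage 4: nutritional or respiratory failure". Table 7 records stages 1 to 4. There is no code for death.
- **Timing.** In Table 1 the row "King's classification of clinical stages of ALS" is marked at V1 and V3 but not at V2. V3 (months 9 to 14) is therefore the only post-baseline value.
- **Comparison.** Section 11 compares secondary endpoints in confirmed SOD1 or C9orf72 carriers with tested patients who have no ALS-associated mutation, and extends this to changes over time. King's stage is among the additional endpoints in section 3.4.2.
- **Analysis set.** Section 11 restricts follow-up analyses to patients with full data. The reason it gives is: "since not all patients are expected to complete end-of-study assessments due to disease progression, e.g., death". It adds that "missing data records will be omitted and treated as missing values".
- **Use of death.** Section 11 plans to compare the proportion of deaths between completers and non-completers. Nothing compares deaths between genotypes. Date of death is an item in Table 4 and a row in Table 1, but that row has no visit marked.
- **Expected completion.** Section 5.1 plans 2,000 recruits and says: "More than 1000 subjects are expected to complete the end-of-study assessments, after an observation period of 12 months".

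**The concern.** In ALS, death is the end of the progression that King's staging describes. Here it is treated as a missing value. Because King's stage is not taken at V2, a patient who dies before V3 contributes nothing after baseline. If genotypes differ in mortality, the groups compared at V3 have been selected to different degrees by the very process under study, and covariate adjustment cannot bring back patients who are not in the analysis set.

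At stake is the stated aim of relating genotype to the course of disease in order to judge the potential of genetic therapies. A faster genotype could appear similar to the reference group, or milder, on a staging result reported with a p-value and a 95% confidence interval.

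**Working it through.** The plan gives no effect size, power or death rate, so there is no figure of its own to reproduce. The steps below bound the loss and show what the stated rules can do.

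**1. Patients without V3 (from section 5.1).** 1 − 1,000/2,000 = 50%. As more than 1,000 are expected to complete, this is an upper bound, and it covers every cause of loss.

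**2. Carriers expected (rates from section 2.1; familial share f of 5% to 10% assumed).**
- SOD1: 2,000 × [0.148f + 0.012(1 − f)] = 37.6 at 5% and 51.2 at 10%.
- C9orf72: 2,000 × [0.34f + 0.05(1 − f)] = 129 at 5% and 158 at 10%.

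**3. Assumptions for the illustration (none from the documents).** Reference survivors at V3 are 15/25/30/30% in stages 1 to 4, so their mean is 0.15 + 0.50 + 0.90 + 1.20 = 2.75. Deaths before V3 are 20% or 30% in the reference group and 40% or 50% in carriers. Death is the only cause of loss. For the means, death is scored 5; the rank test uses only its order.

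**4. Mean stage, reference / carriers.** In pattern A, carrier survivors have the same stage mix as reference survivors. In pattern B, the excess carrier deaths come out of stage 4, then stage 3 once stage 4 is empty.

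| Deaths, ref/carriers | A: survivors only | A: death = 5 | B: survivors only | B: death = 5 |
|---|---|---|---|---|
| 20% / 40% | 2.75 / 2.75 | 3.20 / 3.65 | 2.75 / 2.33 | 3.20 / 3.40 |
| 20% / 50% | 2.75 / 2.75 | 3.20 / 3.875 | 2.75 / 2.12 | 3.20 / 3.56 |
| 30% / 40% | 2.75 / 2.75 | 3.425 / 3.65 | 2.75 / 2.54 | 3.425 / 3.525 |
| 30% / 50% | 2.75 / 2.75 | 3.425 / 3.875 | 2.75 / 2.25 | 3.425 / 3.625 |

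Worked for the first row. A: 0.8 × 2.75 + 0.2 × 5 = 3.20 and 0.6 × 2.75 + 0.4 × 5 = 3.65. B: carriers are 12/20/24/4% in stages 1 to 4 and 40% dead. The survivors' mean is (0.12 + 0.40 + 0.72 + 0.16)/0.60 = 2.33; with death it is 1.40 + 2.00 = 3.40.

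**5. How often a difference is declared** (simulated two-sided Mann-Whitney test at 0.05, 500 runs, 1,800 reference patients, 51 or 130 carriers; first row of the table).
- Pattern A: survivors only, 7% and 3% of runs, about the null rate; death ranked worst, 72% and 97%. Over all four rows, the death-ranked figure runs from 25% to 94% with 51 carriers and from 50% to 100% with 130.
- Pattern B: survivors only, 68% and 96%, with the mean favouring carriers; death ranked worst, 18% and 48%, with the mean against them.

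**6. A milder pattern.** If one underlying severity shift drives both stage and death, carrier survivors still look worse. With 20% reference deaths and a shift of 0.5 SD (carrier deaths 36.6%), the probability that a carrier is worse than a reference patient, counting ties as half, is 0.59 among survivors and 0.63 with death included. Over reference deaths of 10% to 30% and shifts of 0.3 to 0.8 SD, the ranges are 0.55 to 0.65 and 0.58 to 0.70.

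**7. Why adding the deaths alone is not enough.** Suppose half the patients lack V3 and 20% of all patients are dead. Then 30% are alive without V3. Leaving them out gives a share dead of 0.20/0.70 = 28.6% instead of 20%.

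**The case against.** Several points on the other side stand:

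- The plan names no King's test at V3. The comparison follows from the general rules for secondary endpoints and changes over time, so this point concerns what those rules produce.
- The evaluation is exploratory, King's stage is one of many additional endpoints, and the primary endpoint is untouched. Section 11 also acknowledges loss through death and would make it visible overall, though not by genotype.
- Reporting deaths by genotype beside stage among survivors would expose much of the problem and keep King's stage as a plain description of living patients. This belongs in the fix.
- An ordinal model with death on top need not satisfy proportional odds. Suppose 30% of carriers and 15% of reference patients die and 25% of survivors in each group are in stage 4. The odds ratio for death is (0.30/0.70)/(0.15/0.85) = 2.43, and for stage 4 or death it is (0.475/0.525)/(0.3625/0.6375) = 1.59.
- Recording a date of death is not the same as tracing it. Sections 7, 8.1 and 8.2 give no procedure for vital status after a missed visit or withdrawal, so the change goes beyond analysis wording.

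What does not stand is that the exploratory label settles the matter. It limits the consequence, but the selection remains and the results will still carry p-values and confidence intervals.

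**Conclusion.** The point holds as a bias built into a secondary comparison. Under the stated rules, a King's follow-up comparison is conditional on being alive and seen at V3, and no planned analysis by genotype puts the deaths back. The result can be diluted, null or reversed. Which of these occurs depends on death rates and stage distributions that the documents do not give, so its size is unknown.

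Three stronger readings are tempting, and the documents do not support them:

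- *A more lethal genotype will look no worse.* It can, but under a common severity shift the contrast is only weakened.
- *About half the cohort dies before V3.* The 50% is a ceiling for loss from all causes.
- *A particular number of points is lost.* The scenario under objection gives 47.5% against 36.25% for stage 4 or death, a gap of 11.25 points against zero among survivors. But the zero is built in by assuming equal stage mixes, and the gap is just the assumed mortality difference, 0.15 × 0.75.

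**What to change.** In section 11:

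1. Analyse King's follow-up status with death before the end of the V3 window as the worst category, above stage 4. Use a rank-based or ordinal comparison adjusted for baseline stage and the planned covariates (sex, age, intervention history, taken at baseline). If a proportional odds model is used, check that assumption and name the alternative. State which status counts for a patient seen at V3 who dies later in the window.
2. Report beside it the proportion dead by genotype and the stage distribution among survivors.
3. Give the number of living patients without V3 by genotype and state how they are handled, for example in a sensitivity analysis, so that the share dead is not inflated.

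In Table 1, make clear that date of death or vital status is recorded up to the end of the V3 window for patients without a V3 visit. Month 14 is the upper limit in both Table 1 and section 4.3.

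The cost is a little more analysis, some vital-status follow-up at the sites, and a composite that mixes stage with mortality. Reporting both components separately answers the last of these.

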#### **3.3. Additional objectives**

The additional objectives of this study are as follows:

- To investigate the demographic and social characteristics
- To investigate the family history for ALS or FTD
- To investigate the clinical classification, functional deficits, disease progression and health care measures in a subset of ALS patients with pathogenic variants in the genes of SOD1

or C9orf72 as compared to ALS patients with no ALS-associated mutations in the investigated genes

- To register available data on serum concentration of neurofilament light chain (sNfL)
- To register the history of interventions and health care measures including percutaneous endoscopic gastrostomy (PEG) and ventilation therapy
- To register the provision with assistive technology devices, symptomatic pharmacotherapy and physical, occupational and speech therapy
- To identify patient's treatment expectations towards ALS therapy using the Measure Your Medical Outcome Profile (MYMOP2)

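### sNfL is registered from available results with only a pg/mL value specified, and on a schedule that differs by genotype, so assay and timing differences cannot be separated from genotype differences

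*Combined protocol and SAP*

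**What the plan says.** - **Source.** Section 3.3 sets the aim as "To register available data on serum concentration of neurofilament light chain (sNfL"). For patients with an SOD1 mutation, the notes to Table 1 (section 1) provide for "up to monthly collection of existing data of sNfL". Sections 8.1 and 8.2 do not list sNfL among the data sources, and the laboratory named in section 8.3 is for the genetic analysis.
- **Data item.** Table 7 (section 9.6.3) lists only "Serum concentration of neurofilament light chain (sNfL) in pg/mL".
- **Schedule.** The Table 1 windows are "V1 M1-M3 (Baseline"), "V2 M4-M8* (Follow-Up") and "V3 M9-M14 (Closure"). The notes add: "In the main cohort of non-SOD1 patients the collection of sNfL data is limited to the visits V1 (baseline) and V2 (follow-up").
- **Analysis.** Section 11 does not name sNfL. Its general rule is: "The SMD of each measure over up to 12 months will be estimated using the change in measure between each subject's assessments". It states no transformation. It also lists medians, quartiles, Kruskal-Wallis and Mann-Whitney tests, and linear regression adjusted for unspecified confounders. The covariates it names for longitudinal results are sex, age and intervention history.
- **Comparison.** Sections 3.3 and 11 compare SOD1 and C9orf72 carriers with patients who have no mutation in the tested genes, both at baseline and over time.

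**The concern.** sNfL is the only biomarker endpoint, and up to about 18 centers may contribute values. Two things other than genotype can move the comparison.

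The first is measurement. If assays read differently and carriers are not spread over assays as the reference group is, the assay difference appears as a genotype difference. If a patient's assay changes between visits, the apparent change is partly the assay. A result that already existed may also have been sampled well before the visit under which it is entered. Without assay, laboratory and sampling date in the dataset, the analyst cannot adjust for any of this.

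The second is follow-up length. SOD1 patients contribute later sNfL values than everyone else. A rule that takes change over as long as 12 months can therefore use different intervals in the two groups being compared.

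At stake is how any reported sNfL difference between genotypes is read.

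**Working it through.** The plan gives no power, effect size or SD for sNfL, so there is no figure of its own to reproduce. The calculations below show possible size only. Assay factors, assay split, SDs and drift are assumptions.

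**1. Group sizes.** Inputs are 2,000 subjects (section 5.1) and SOD1 in 14.8% of fALS and 1.2% of sALS (section 2.1). The fALS share is assumed to be 5% or 10%.
- 5%: 2,000 × (0.05 × 0.148 + 0.95 × 0.012) = 37.6
- 10%: 2,000 × (0.10 × 0.148 + 0.90 × 0.012) = 51.2
- C9orf72: 2,000 × 0.065 = 130
- Reference group, ignoring FUS and TARDBP: 2,000 − 51 − 130 = 1,819

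**2. False ratio from assay.** Let one assay read k times the other, with 80% of carriers and 40% of the reference group on the higher-reading one. With no true difference, the ratio of geometric means is exp((0.8 − 0.4) × ln k). The chance of p < 0.05 by Mann-Whitney was simulated with 40 carriers, 800 reference patients and log-SD 0.7.

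| Assay factor k | False ratio | Mann-Whitney p < 0.05, no true difference |
|---|---|---|
| 1.2 | 1.08 | about 9% |
| 1.5 | 1.18 | about 28% |
| 2.0 | 1.32 | about 61% |

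A z-test on log values with 51 versus 1,819 patients and log-SD 0.8 gives 7%, 15% and 33% for a 25-point imbalance in assay use, and 13%, 43% and 86% for a 50-point imbalance. With a common assay, or full adjustment for assay, the rate is 5%.

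**3. Within-person change.** A move to the higher-reading assay adds a false change of k − 1, that is 20%, 50% or 100%. If the assay stays the same, log(k·x₂) − log(k·x₁) = log(x₂/x₁), so the factor cancels on the log scale. On the raw scale the change becomes k(x₂ − x₁), and it does not cancel.

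**4. Timing.** From the Table 1 windows:
- V1 to V2: 4 − 3 = 1 month to 8 − 1 = 7 months
- V1 to V3: 9 − 3 = 6 months to 14 − 1 = 13 months, with sNfL at V3 in SOD1 patients only

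Take a gap of about 12 − 6 = 6 months and the same drift per month in both groups, in units of the SD of change. The false SMD is 6 × drift. The SE is √(1/51 + 1/1,819) = 0.142.

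| Drift per month | False SMD | p < 0.05, 51 vs 1,819 | p < 0.05, 26 vs 910 |
|---|---|---|---|
| 0.02 | 0.12 | 14% | 9% |
| 0.05 | 0.30 | 56% | 33% |
| 0.10 | 0.60 | 99% | 86% |

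The last column halves the groups to reflect about 1,000 completers. C9orf72 carriers follow the non-SOD1 schedule, so this timing problem is confined to SOD1.

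**5. Scale.** For log-normal values, 40 versus 800 patients, a true ratio of 1.4 and 4,000 simulations, power on baseline levels is:

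| Log-SD | Welch, raw | Welch, log | Mann-Whitney |
|---|---|---|---|
| 0.6 | 84% | 92% | 92% |
| 0.7 | 66% | 83% | 83% |
| 0.9 | 31% | 62% | 61% |

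The rank test recovers the power lost on the raw scale, but step 2 shows that it does not remove assay confounding.

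**The case against.** Several stronger readings are tempting, and the documents do not support them.

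- **That the plan analyses sNfL as a raw mean change.** Section 11 never assigns a method to sNfL. It lists medians and rank tests, and ties the t-test to ALS-FRS and MYMOP. What stands is that no transformation is stated, so the default SMD, and any regression, would use untransformed values.
- **That precision is lost whatever test is used.** Step 5 shows otherwise. The loss belongs to the untransformed SMD and regression route.
- **That the missing information can never be recovered.** Section 10.1 requires source data to be available for audit, and section 10.2 has the eCRF track visits. Tables 7 and 9 list no date for ALS-FRS or MYMOP either, so an unlisted date does not prove that none is stored. Retrospective tracing may be possible. A visit date, however, is not the sampling date of an existing result.
- **That several assays are in use, or that carriers cluster by center.** Neither is stated. The assay figures show what could happen, not what will.
- **That the study takes no sNfL sample of its own.** The wording on existing data is attached to the SOD1 subgroup; for the whole cohort section 3.3 speaks of available data. The source is simply not specified further.

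It is also fair that age is already a named covariate, and that the general clause on confounders could be read to cover assay. That clause works only if assay is in the dataset. Center is known and could serve as a proxy, but 51 SOD1 carriers over 18 sites is about 3 per site, and center does not reveal a change of assay within a site. Finally, sNfL is one of many additional endpoints and no formal hypothesis is tested.

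**Conclusion.** The point holds in a limited form. With the data items and covariates now listed, an sNfL difference between genotypes could not be told apart from a difference in assay or timing.

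The timing part rests on the protocol's own schedule, and only its size depends on an assumed drift. The assay part is conditional: it needs more than one assay and an uneven spread of assays over genotypes. Under the assumed 80%/40% split the false ratio is 1.08 to 1.32 for assay factors of 1.2 to 2.0. It is nil if all values come from one assay.

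The endpoint is exploratory and the primary genetic frequencies are unaffected. The change is still worth making, because it is small and is easier to make during collection than by tracing results afterwards.

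**What to change.** 1. Add to Table 7 and the eCRF, for each sNfL value: sampling date, measuring laboratory and assay platform.
2. Count a value as V1 or V2 only if it was sampled in that visit's window.
3. Compute within-person change only between samples measured with the same assay.
4. State in section 11 that log(sNfL) is analysed with age, assay/laboratory and, for change, actual time between samples as covariates, and that results are reported as geometric-mean ratios with 95% confidence intervals.
5. Compare genotypes on the shared V1-V2 interval. Use later SOD1 values only descriptively, or in a model with actual time.

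The cost is three fields per value and a short addition to section 11. For results already entered, the fields would have to be traced from source records. The downside is that some out-of-window or cross-assay values drop out of the change analysis, which matters most in the small SOD1 group.
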